### 3.2.12 Extent of Exposure

The duration of treatment for each subject will be evaluated by calculating the number of days on therapy. The range and mean for days on therapy will be calculated for the ASaT population.

### 3.2.13 Cross Treated Subjects

The following data analysis conventions will be used for cross treated subjects:

#### Safety Analysis:

- Scenario 1: if the incorrect kit corresponded to the assigned treatment arm then the subject will be analyzed to the group randomized (no issue).
- Scenario 2: If the subject incorrectly **switched from active to placebo** then the subject will be analyzed in the active treatment arm (conservative approach).
- Scenario 3: If the subject incorrectly **switched from placebo to active** then the subject will be analyzed in the active treatment arm (conservative approach).

For subjects that incorrectly switched from placebo to active, they will be excluded from the by-time-adverse event analyses.

For any adverse experiences (AE) occurring during the period that the incorrect study medications were taken, the cross-treatment information will be provided in the by-subject-listing of AEs and the narratives if the subject had a serious AE or discontinued from the study due to an AE.

#### Subject Compliance / Extent of Exposure:

The cross-treated information will be included in the clinical study report (CSR). The actual study drug exposure information within the clinical database for these subjects will be used to calculate the subject compliance and the duration of treatment presented in the relevant CSR tables (eg, Extent of Exposure), with the days exposed to the incorrect study drug being treated as days not exposed / non-compliant to the randomized treatment.

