#### **3.2.4.2 Safety Analysis Populations**

The All-Subjects-as-Treated (ASaT) population will be used for the analysis of safety data in this study. The ASaT population consists of all randomized subjects who received at least one dose of study treatment. Subjects will be grouped by the study treatment actually received.

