### 3.2.11 Compliance (Medication Adherence)

For each subject, percent compliance will be calculated using the following formula:

$$\text{Percent Compliance} = \frac{\text{Number of Days on Therapy}}{\text{Number of Days Should Be on Therapy}} \times 100\%$$

A day within the study will be considered an “On-Therapy” day if the subject takes all required medication as instructed in Section 5.2 of the protocol. When a subject takes less than or more than the required medication on a day, that day is not considered an On-Therapy day.

For subjects who are followed for the entire study period, the “Number of Days Should be on Therapy” is the number of days from the first scheduled treatment day to the last scheduled treatment day. For subjects who discontinue from the study, the “Number of Days Should Be on Therapy” is the number of days from the first scheduled treatment day to the last dose day.

Summary statistics will be provided on percent compliance for the ASaT population.

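### For subjects switched by mistake from placebo to active, the sSAP's exposure rule counts their placebo days and drops their active days, although they are analysed in the active arm

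*SAP*

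**What the plan says.** Four parts of the sSAP bear on this.

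- **Arm for safety (SAP 3.2.13, Safety Analysis, Scenario 3):** "If the subject incorrectly switched from placebo to active then the subject will be analyzed in the active treatment arm". Scenario 2, the switch from active to placebo, also goes to the active arm.
- **Grouping of the safety population (SAP 3.2.4.2):** "Subjects will be grouped by the study treatment actually received".
- **Exposure and compliance outputs:** duration of treatment is the number of days on therapy, and "The range and mean for days on therapy will be calculated for the ASaT population" (SAP 3.2.12). For adherence, "Summary statistics will be provided on percent compliance for the ASaT population" (SAP 3.2.11).
- **Counting rule for cross-treated subjects (SAP 3.2.13, Subject Compliance / Extent of Exposure):** actual drug exposure from the clinical database is used for both compliance and duration of treatment, "with the days exposed to the incorrect study drug being treated as days not exposed / non-compliant to the randomized treatment".

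**The concern.** One counting rule serves two different quantities. Compliance asks how well a subject kept to the randomised treatment, so it is right to count days on the wrong kit as non-compliant. Extent of exposure in a population grouped by treatment received asks how long the subject took the drug of the column in which he or she is shown.

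For Scenario 3 the two questions have opposite answers. The subject is displayed under active, the incorrect drug is active, and the rule removes exactly the days that the active column is meant to count. The subject's adverse events are attributed to active, while the duration shown beside them is time on placebo. The exposure table is descriptive, but readers use it as context for the safety results.

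**Working it through.** The documents state no exposure figure for cross-treated subjects, so there is nothing to reproduce. The check applies the rules to one subject.

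**Inputs from the documents**
- Treatment lasts about 20 to 28 weeks (Protocol 2.1), that is 140 to 196 days.
- Kits are monthly (Protocol 9.2).
- About 1000 subjects are randomised 1:1, so about 500 per arm (SAP 3.2.8).

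**Assumptions**
- One tablet is taken on every day of the course.
- One wrong kit means about 28 days on active.
- The number of cross-treated subjects is varied from 1 to 25, because the documents do not give it.

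**Rule applied to one Scenario 3 subject.** Let T be the treated days, of which a were on active and T − a on placebo.
- Days on therapy under SAP 3.2.13 = T − a, because the a days on the incorrect drug are removed.
- Percent compliance = (T − a)/T.
- True days on active = a.
- Error in the active column = (T − a) − a = T − 2a.

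| T | a (true active days) | Days credited | Error | Credited as % of T | True active as % of T |
|---|---|---|---|---|---|
| 196 | 28 | 168 | +140 | 85.7 | 14.3 |
| 196 | 98 | 98 | 0 | 50.0 | 50.0 |
| 196 | 168 | 28 | −140 | 14.3 | 85.7 |
| 140 | 28 | 112 | +84 | 80.0 | 20.0 |
| 140 | 112 | 28 | −84 | 20.0 | 80.0 |

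The error is positive when the switch was short, negative when it was long, and zero only when half the course was on each drug.

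**Scenario 2 for comparison.** A subject switched from active to placebo is shown under active. The placebo days are removed as incorrect, and the active days remain. Here the rules agree, so the mismatch is confined to Scenario 3.

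**Effect on the active-arm mean.** If k such subjects join 500 others, the shift is k × (T − 2a)/(500 + k). With T = 196 and a = 28:
- k = 1: 140/501 = 0.3 day
- k = 5: 5 × 140/505 = 1.4 days
- k = 10: 10 × 140/510 = 2.7 days
- k = 25: 25 × 140/525 = 6.7 days

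With a = 168 the shifts have the same size and the opposite sign. With T = 140 and a = 28, five subjects give 5 × 84/505 = 0.8 day. With an assumed 180-day course, 30 active days and five subjects within an arm of 500, the shift is 5 × (150 − 30)/500 = 1.2 days.

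**The case against.** **The column is not named.** The active-arm rule stands under the Safety Analysis sub-heading of SAP 3.2.13. The exposure paragraph has its own sub-heading and refers only to the randomised treatment. If the sponsor meant to show these subjects under their randomised arm, the counting would be coherent: placebo days under placebo, wrong-kit days removed. This stands in part. The active column is inferred from the ASaT grouping, the population named for exposure and compliance, and Scenario 3. Display by randomised arm is not stated, however, and would conflict with the ASaT grouping. It would also leave the real active days in neither column.

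**Recorded intake is used.** The paragraph starts from actual drug exposure, but the same sentence then sets days on the incorrect drug to not exposed, so this does not rescue the rule.

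**There are safeguards.** Scenario 3 subjects are left out of the by-time adverse event analyses. For events in the wrong-kit period, cross-treatment is shown in the by-subject listing, and in the narratives for serious events or discontinuations due to adverse events. Cross-treatment information also goes into the CSR. These steps reduce the risk of misreading but do not correct the exposure figures.

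**Stronger readings that the documents do not support.**
- A reader might infer that the whole active arm's exposure is inverted. Only the Scenario 3 subjects' own values are.
- A reader might take the exposure table as the denominator of the safety rates. Tier 1 and Tier 2 adverse event endpoints are proportions of subjects (SAP 3.2.5.2), and no person-time analysis is planned.
- A reader might expect the reported range to be badly wrong. Credited days stay between 0 and T, and with 15% dropout assumed, short durations are probably present anyway. An effect on the range is possible but cannot be shown.
- SAP 3.2.11 also says "When a subject takes less than or more than the required medication on a day, that day is not considered an On-Therapy day", so extra-tablet days drop out of duration too. That concerns all subjects in both arms and is a separate matter from cross-treatment.

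**Conclusion.** The point holds for Scenario 3 subjects. As written, each contributes to the active-arm exposure summary the complement of his or her true active exposure: T − a days instead of a, for example 168 against 28 in an assumed 196-day course. The percent compliance shown for such a subject under active is likewise adherence to placebo. That is a legitimate measure against the randomised treatment, but it does not describe active intake.

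The conclusion rests on reading the display column as active, which follows from the ASaT rules but is not stated in the exposure paragraph. The error can be large for one subject and is small for the arm: about 1.2 to 1.4 days on the mean for an assumed five subjects in about 500, under the 180- and 196-day illustrations. It matters more only if many subjects were cross-treated. Adverse event proportions, tests, confidence intervals and the FAS efficacy analysis are unaffected.

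**What to change.** Split the counting rule in SAP 3.2.13 in two.

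1. **Percent compliance:** keep days on the incorrect drug as non-compliant with the randomised treatment, and label the summary as compliance with randomised treatment. The compliance rule itself does not change.
2. **ASaT extent of exposure:** state the arm in which each cross-treated subject is displayed, and count days on that arm's drug. For Scenarios 2 and 3 these are the active days. Show days on the other drug separately in a footnote or listing.

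Any change to how days with more than one tablet count towards exposure should be decided separately and applied equally to both arms.

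The cost is one sSAP sentence and a small programming change. The sSAP says that actual drug exposure for these subjects is in the clinical database, so no new data are needed.

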#### Efficacy Analysis:

No impact for the FAS analysis. As pre-specified in the protocol, subjects will be included in the Full Analysis Set (FAS) population and will be analyzed according to the treatment group to which he/she was randomized.

## APPENDIX: Technical Details for supplemental SAP

### APPENDIX A

#### CONSTRAINED LONGITUDINAL DATA ANALYSIS (CLDA) METHOD (WITH ADJUSTMENT FOR BASELINE VALUES) – TECHNICAL DETAILS FOR MODEL SPECIFICATION, ASSUMPTIONS, AND SAS IMPLEMENTATION CODES

##### Model

Let  $Y_{ijt}$  be the response for subject  $i$ , with treatment assignment  $j$ , at time  $t$ . The marginal mean responses of the cLDA model can be formulated as

$$E(Y_{ij0}) = y_0, \quad j = 0, 1.$$

and

$$E(Y_{ijt}) = y_0 + y_{jt}, \quad j = 0, 1; t = 1, 2, 3, 4.$$

The mean response  $\gamma_0$  at  $t = 0$  is constrained to be the same for all treatment groups due to randomization. The effect  $\gamma_{jt}$  denotes the change from baseline for treatment  $j$  at time  $t$ . The cLDA model assumes that baseline and post-baseline values have a joint multivariate normal distribution. A Toeplitz covariance matrix can be specified in the mixed model to account for within subject correlation at times  $t \geq 0$  (including baseline).

At each time point  $t$ ,  $t = 1, 2, 3, 4$ , the mean change from baseline (LSMEANS) for  $j^{\text{th}}$  dose of test drug and control are  $\gamma_{jt}$  and  $\gamma_{0t}$ , respectively, as defined in the cLDA model above.

The treatment difference for  $j^{\text{th}}$  treatment group vs. control for the mean change from baseline at time point  $t$ ,  $t = 1, 2, 3, 4$  is defined as:

$$\eta_{jt} = Y_{jt} - Y_{0t}.$$

This longitudinal model provides valid statistical inference in the presence of possible missing data if the missing data mechanism is ignorable (or more specifically, missing at random [MAR] or missing completely at random [MCAR]). This missing data mechanism requires that the probability of a data point being missing does not depend on the missing data after adjusting for the observed data.

Reasons for discontinuation from the trial may include lack of efficacy, clinical or laboratory adverse experiences, relocation, withdrawal of consent, protocol violations, and/or data processing issues. Missing data caused by relocation and data processing issues, are likely to be MCAR. On the other hand, missing data caused by discontinuation due to lack of efficacy may belong to MAR because the discontinuation may depend on the observed efficacy outcomes. The

MAR or MNAR mechanisms might each underlie the other reasons to some extent. If treatment in large part determines the loss of data for these other reasons (such as clinical or laboratory adverse experiences), the mechanism may be close to MAR since treatment assignment is an observed variable and included in the analysis model. Based on the prior trial results, missing data due to other reasons is relatively infrequent.

### **Model Convergence**

If the Toeplitz covariance model fails to converge with the default algorithm, then the AR(1) structure can be used to provide initial values of the covariance parameters.

### **Example SAS Codes**

```
*****.  
** data step necessary prior to running SAS PROC MIXED;  
*****; DATA long; SET long;  
ARRAY T{5} t0-t4; * time indicator variables; ARRAY TT1{5} tt10-tt14;  
  
** define week times treatment 1 indicator variables; DO i = 1 TO 5;  
t{i} = (time=(i-1));  
tt1{i} = t{i}*(trt=1);  
tt2{i} = t{i}*(trt=2);  
END; DROP i; RUN;
```

```
*****.  
** fitting the cLDA model using SAS PROC MIXED;  
*****; PROC MIXED DATA=long;  
  
CLASS subj time stratum; ** subj is the subject id number **; MODEL y=time tt11 tt12 tt13 tt14 tt21 tt22 tt23 tt24 stratum;  
REPEATED time / SUBJECT=subj TYPE=TOEP;  
  
ESTIMATE 'T1 Diff (MK - Placebo)' tt11 1; ESTIMATE 'T2 Diff (MK - Placebo)' tt12 1; ESTIMATE 'T3 Diff (MK - Placebo)' tt13 1;  
ESTIMATE 'T4 Diff (MK - Placebo)' tt14 1;  
  
ESTIMATE 'T1 Placebo LSM' time -1 1 0 0 0;  
ESTIMATE 'T2 Placebo LSM' time -1 0 1 0 0;  
ESTIMATE 'T3 Placebo LSM' time -1 0 0 1 0;  
  
ESTIMATE 'T4 Placebo LSM' time -1 0 0 0 1;  
  
ESTIMATE 'T1 MK LSM' time -1 1 0 0 0 tt11 1;  
ESTIMATE 'T2 MK LSM' time -1 0 1 0 0 tt12 1;  
ESTIMATE 'T3 MK LSM' time -1 0 0 1 0 tt13 1;  
ESTIMATE 'T4 MK LSM' time -1 0 0 0 1 tt14 1;  
  
ODS OUTPUT Estimates=outm1; RUN;
```
